7.3.4 Replacement of withdrawn patients

Patients withdrawn from the study will not be replaced.

7.3.5 Screen failures

Screen failures are defined as patients who consent to participate in the clinical study but are not subsequently randomized into the study. A minimal set of screen failure information is required which includes demography, reason/s for screen failure, eligibility criteria, and any SAE.

Patients who do not meet the criteria for participation in this study (screen failure) may be rescreened for a later flare. Rescreened patients should keep the same study specific patient ID as for the initial screening.

7.3.6 Patients with data collection failure for primary endpoint

Patients with data collection failure for primary endpoint are defined as patients who are randomized in the clinical study but have no values collected for patient-assessed pain intensity from baseline to 72 hours for the first flare. These patients will however continue in the study and be included in the ITT and safety populations.

For each primary endpoint collection failures, one extra patient can be randomized in the study. Maximum 10 extra patients can be randomized under this protocol.

7.4 Treatments

7.4.1 Treatments administered

The patients will receive IMPs according to the randomization schedule, Table 1.

Table 1 Investigational medicinal products

Arm	Investigational product	Dosage form	Route	Daily dose	Dosage regimen
A	Anakinra	Solution	s.c. injection	100 mg	Once daily for 5 days
	Anakinra placebo	Solution	s.c. injection	-	Once daily for 5 days
	Triamcinolone placebo	Solution	i.m. injection	-	Single injection
B	Anakinra	Solution	s.c. injection	100 mg	Once daily for 5 days
	Anakinra	Solution	s.c. injection	100 mg	Once daily for 5 days
	Triamcinolone placebo	Solution	i.m. injection	-	Single injection
C	Anakinra placebo	Solution	s.c. injection	-	Once daily for 5 days
	Anakinra placebo	Solution	s.c. injection	-	Once daily for 5 days
	Triamcinolone	Solution	i.m. injection	40 mg	Single injection

7.4.2 Identity of investigational medicinal products

The investigational product anakinra is delivered as a sterile solution for injection, prefilled in a single-use syringe with the strength 100 mg. The total volume of injection is 0.67 mL and the

concentration of anakinra in the solution is 150 mg/mL. The prefilled syringe has a pre-attached 29 Gauge thin wall half inch needle, a rubber plunger and a latex free rigid needle shield.

The matching placebo for anakinra is delivered as a sterile solution for injection in a single-use prefilled syringe identical to the anakinra syringe. The placebo consists of the active product vehicle (0.67 mL) but without the active ingredient anakinra.

The anakinra drug substance is manufactured by [REDACTED] and drug product and matching placebo for anakinra are manufactured [REDACTED]

The registered triamcinolone (Kenalog®) will be used as reference product and a matching placebo triamcinolone will be prepared for this study. The triamcinolone acetone placebo is manufactured by [REDACTED]

The reference product, triamcinolone acetone (Kenalog®), is delivered in vials containing a 40 mg/mL solution, 1 mL for i.m. injection.

The matching placebo for triamcinolone acetone injectable suspension is manufactured as an emulsion to have the same appearance as the reference product. The triamcinolone acetone placebo will be prepared by diluting commercially available lipid emulsion with physiological saline to obtain a white emulsion with appropriate tonicity for i.m. injection. The obtained emulsion is identical in appearance as the comparator suspension. The triamcinolone acetone placebo is delivered in a vial and stopper identical to the triamcinolone acetone vial and stopper. However, the colour of the caps on the Kenalog vials and the corresponding placebo vials might not be identical during the whole study duration (see section 7.4.6.2 regarding the role of the unblinded pharmacist/nurse).

Labeling will comply with national regulatory requirements.

Possible deficiencies related to the quality or identity of the investigational products should be reported both to the CRO study monitor and also directly to [contact].

7.4.3 Storage of IMP

The IMP (anakinra or placebo prefilled syringes) must be stored at refrigerated conditions at 2-8 °C (36°-46°F) in a secure area at the study center. The investigational product should be kept in its original carton and away from light. The IMP should not be frozen or shaken.

Possible deficiencies related to site distribution or storage of IMP should be reported in accordance with instructions provided in the IMP handling manual.

For more details, see also 7.4.6.

7.4.4 Method of assigning patients to a treatment group

The patients will be randomized to treatment with 100 mg anakinra, 200 mg anakinra or 40 mg triamcinolone in a 1:1:1 ratio.

The randomized groups will be as follows:

Arm A: anakinra 100 mg,

Arm B: anakinra 200 mg

Arm C: triamcinolone 40 mg

An IWRS will be used for the randomization. Biostatistics at Perceptive will generate the randomization scheme for the IWRS, which will link sequential patient randomization numbers to treatment codes.

The randomization will be stratified by ULT use (yes/no) and BMI (<30.0 or ≥30.0 kg/m²) at inclusion.

The randomization numbers will be generated in blocks. Within each block, equal numbers of patients will be allocated to each treatment group. The block size will not be revealed before breaking of the blind.

A separate IWRS manual will be provided to the investigators.

7.4.5 Selection of doses

Refer to Section 7.2.4.1, 7.2.4.2 and 7.2.4.3 for the rationale for the selected dosage regimen, dose levels and treatment duration. The rationale for the choice of reference product is presented in Section 7.2.3.

7.4.6 Selection and timing of doses for each patient

7.4.6.1 Home storage and transportation

The Day 1 IMP injections will be administered at the hospital/clinic. Patients who are then discharged from the hospital or clinic, will get IMP for the next two days (Day 2 and 3) to be injected at home. The patients will return to the hospital/clinic Day 4 and the fourth dose of IMPs will be administered at site. When the patients return home they will get the IMP for the next day (Day 5) to be injected at home. The IMP will be transported by the patients to their homes in provided cold packs. The IMPs should be kept refrigerated at home in its original cartons and protected from light. The IMPs should not be frozen or shaken during storage.

7.4.6.2 Preparation and dosage

Anakinra and matching placebo

At each day of IMP administration period (Days 1 to 5), the anakinra and/or matching placebo will be given as two (2) s.c. injections of 0.67 mL solution in single-use prefilled syringes for s.c. injection.

30 minutes before injection, the prefilled syringes should be taken out from cold storage to equilibrate the injection solution with room temperature.

Triamcinolone and matching placebo

At Visit 1 of each flare, the triamcinolone or matching placebo will be given as one (1) i.m. 1 mL injection withdrawn with a syringe from a vial containing a 40 mg/mL solution. The vial should be shaken before use to ensure a uniform suspension. Prior to withdrawal, the suspension should be inspected for clumping or granular appearance (agglomeration). An agglomerated product results from exposure to freezing temperatures and should not be used.

In addition to the above instructions, a separate study drug handling manual will be provided. The manual will include working instructions for unblinded pharmacist/nurse responsible for removal of the triamcinolone/placebo vial caps if the caps differ in colour. The unblinded pharmacist/nurse must not be involved in the conduct of the study. The study monitor will inform the Investigator/Study Coordinator if an unblinded procedure is needed.

7.4.6.3 Administration

The IMP administration will be initiated on the day of randomization (Visit 1) and the administrations scheduled for the first day of each flare will be supervised or given by the investigator (or delegated study staff) at the out-patient clinic, emergency department (ED) or hospital. If the patient is treated by an out-patient clinic or is discharged from ED/hospital before the end of 5-day IMP administration period, the daily s.c. injections at 24, 48 hours and Day 5 will be administered at home by the patient themselves or a caregiver.

At the 72-hour visit (Day 4, Visit 2), the IMP administration will be supervised or given by the investigator.

Instructions on appropriate use should be given by the investigator to the patient or caregiver. Patients or caregivers should not be allowed to administer any IMP until the patient or caregiver has demonstrated a thorough understanding of procedures and an ability to inject the IMP correctly. A patient leaflet with detailed instructions on the handling, injection and disposal of IMP will be handed out.

Anakinra and matching placebo

The IMP should be administered using subcutaneous injections into fat tissue.

The used syringes should be disposed of and the patients will receive disposal boxes for at home use.

Triamcinolone and matching placebo

For systemic therapy, injection should be made deeply into the gluteal muscle. For adults, a minimum needle length of 1½ inches is recommended. In obese patients, a longer needle may be required.

Throughout each treatment period, the actual number of IMP administrations and timepoint of each administration will be recorded in the eCRF or the patient diary.

7.4.7 Blinding

The first part of the study, i.e. treatment and follow-up of the patients' first flare, is double-blind. Treatment assignment will be blinded for the patients, the investigators and any personnel involved with the study conduct or evaluation at the investigational sites, CRO and sponsor.

Until all patients have completed the Day 15 visit of the first flare (Visit 4), the randomization scheme will only be disclosed to selected CRO personnel to ensure correct packaging of the IMP and correct set-up of the IWRS. The disclosure of the randomization scheme and any individual patient's treatment assignment will be protected by standard operating procedures (SOPs) of the CRO.

When all patients have completed the Day 15 visit of the first flare, collected data up to this date will be analysed by the Sponsor. Blinding will be maintained for patients, investigators, site staff, CRO and applicable vendors throughout the extension phase to prevent any bias in data handling. The Sponsor will take no part in the operational conduct of the study during the extension phase. Details of this process will be outlined in the "Process guideline data integrity document"

Unblinding, i.e., breaking the code for an individual patient during the study, is restricted to emergency situations and should only be used under circumstances where knowledge of the treatment is necessary for the proper handling of the patient. The decision to break the code must be made by the investigator. The study monitor and sponsor must as soon as possible be informed about the code break.

Unblinding should be documented according to instructions in the IWRS manual.

7.4.8 Prior and concomitant therapy

For a list of medication restricted or prohibited (including timeframe) before randomization, see Appendix 1. Other therapy considered necessary for the patient's welfare may be given at the discretion of the investigator.

All therapy taken within specified timelines (see below) prior to and up to 30 days after first IMP administration of each treated flare will be recorded in the eCRF:

- 3 months: treatment with amiodarone, digitoxin, leflunomide, and amphotericin
- 1 month: all other prescription drugs
- 1 week: herbal products, vitamins, minerals, and over-the-counter medications

No other medicinal product under investigation may be used during the study.

Live vaccines should not be given concurrently with anakinra.

Patients are allowed to take urate lowering therapy (ULT) during the study. To be eligible for study participation, the patients should be on a stable dose and regimen for ≥ 2 weeks prior to randomization and expected to remain on a stable dose and regimen for ≥ 2 weeks after study start. During the study, initiation or change of dose and regimen of ULT treatment are allowed after the pain assessment at Day 15 of each flare. The treatment should follow ACR guidelines for ULT (13).

Concomitant pain medication will be restricted and only rescue medication will be allowed, see 7.5.5.4.

7.4.9 Treatment compliance

The date and time of the IMP administrations on Day 1 (Visit 1) and Day 4 (Visit 2) will be recorded in the eCRF. The date and time of the IMP administrations on Days 2, 3 and 5 will be recorded in the patient diary.

7.4.10 Overdose management

For this study, any dose of IMP greater than dose prescribed will be considered an overdose. No dose-limiting toxicities have been observed during clinical trials. No specific treatment is indicated for IMP overdose. If an overdose of IMP is administered, the actual dose taken should be recorded in the eCRF, and any untoward medical occurrence associated with an overdose should be recorded the same way as any adverse event (see section 7.5.6.1).

7.5 Efficacy and safety assessments

7.5.1 Study schedule

7.5.1.1 Schedule of events

See appendix 2.

7.5.1.2 Pre-screening (optional)

Pre-screening is optional and may be done to identify patients that fulfil the study eligibility criteria with the exception of having a current flare of gouty arthritis.

When a pre-screened patient reports a flare of gouty arthritis, the procedures for the baseline visit (Visit 1) will be followed.

7.5.1.3 Baseline, Visit 1

A signed informed consent form must be obtained from the patient prior to any study-related activities. Once the ICF has been signed, the patient will be assigned an enrollment number.

Any SAE that occur after informed consent has been signed must be reported (see Section 7.5.6.1.4).

Data will be collected on medical and surgical history (see Section 7.5.2), prior and concomitant medication (see Section 7.4.8) and demographics (see Section 7.5.4).

Medical examination of current flare (see 7.5.3), local screening laboratory safety assessments (see Section 7.5.6.2), vital signs and physical examination (see Section 7.5.6.3) and a 12-lead ECG (see Section 7.5.6.4) will be performed.

The joint that is most affected, i.e. most painful, will be defined as the index joint and the patient will assess the pain intensity in the index joint on a VAS and Likert scale. These pain assessments will be done as close as possible to randomization and will serve as baseline values.

Once all inclusion and exclusion criteria have been reviewed and recorded (see Section 7.3) and the patient has been found eligible, the patient will be randomized and assigned a randomization number.

Prior to the first IMP administration, blood will be collected for central laboratory safety assessments (see 7.5.6.2), CRP and SAA(see 7.5.5.6), immunogenicity assessments (see 7.5.6.5), exploratory inflammatory biomarkers (see 7.5.8), exploratory pharmacogenetic markers (see 7.5.8.3) and IL-1Ra/anakinra serum concentration assessments (see 7.5.7). The patient assessment of health related quality of life (SF-36® and EQ-5D-5L), the physician's assessment of clinical signs will be performed (see 7.5.5).

Once all predose assessments have been completed, the IMP (i.m. and s.c. injections) will be supervised or administered by the investigator. If the patient or a caregiver is to administer subsequent s.c. injections at home, detailed instructions will be given before discharge (not applicable if patient is hospitalized) (see 7.4.6.3) and IMP for Days 2 and 3 will be provided to the patient.

The patient will be given detailed instructions on how to use the patient diary to record pain intensity (VAS and Likert scale), IMP administration and intake of rescue medication. The patient will also be instructed on the use of permitted rescue medication.

Adverse events, both serious and non-serious, will be recorded from the time point of the first IMP administration (see 7.5.6.1).

For subsequent flares, Visit 1 will not include the informed consent procedure, randomization and recording of demographic data (except body weight).

7.5.1.4 Follow up by telephone at 24 and 48 hours (reminder calls)

Follow up telephone calls to remind the patient to complete the pain intensity assessments and to record the IMP-administration and intake of any rescue medication will be made at 24±2 hours and at 48±2 hours after the first IMP administration.

7.5.1.5 72-hour, Visit 2

Visit 2 will occur 72±4 hours after the first IMP administration of each flare (Day 4).

Vital signs will be recorded and data will be collected on concomitant medication including rescue medication. Adverse events will be recorded.

The compliance with the instructions for how to use the patient diary will be reviewed.

Prior to the IMP administration, blood will be collected for central laboratory safety assessments, CRP and SAA, exploratory inflammatory biomarkers and IL-1Ra/anakinra serum concentration assessments. The patient's assessment of pain intensity, the patient's global assessment of response to treatment, the physician's global assessment of response to treatment, the physician's assessment of clinical signs will be performed

Once all predose assessments have been completed, the IMP (s.c. injections) will be supervised or administered by the investigator.

If the patients is to take the remaining s.c. injection at home, IMP for Day 5 will be provided to the patient.

7.5.1.6 Day 8, Visit 3

Visit 3 will occur 1 week after the first IMP administration of each flare (Day 8±1 day).

The patient's assessment of pain intensity, the patient's global assessment of response to treatment, physician's global assessment of response to treatment, the physician's assessment of clinical signs will be performed.

The patient's assessment of health related quality of life (SF-36® and EQ-5D-5L), will be performed and the health care resource utilization including WPAI:SHP will be recorded.

Vital signs will be recorded and data will be collected on concomitant medication including rescue medication. Adverse events will be recorded.

The compliance with the instructions for how to use the patient diary will be reviewed.

Blood will be collected for central laboratory safety assessments, CRP and SAA, immunogenicity assessments, and IL-1Ra/anakinra serum concentration assessments.

7.5.1.7 Day 15, Visit 4

Visit 4 will occur 2 weeks after the first IMP administration of each flare (Day 15±1 day).

The patient's assessment of pain intensity, the patient's global assessment of response to treatment, physician's global assessment of response to treatment, the physician's assessment of clinical signs will be performed.

The patient's assessment of health related quality of life (SF-36® and EQ-5D-5L), will be performed and the health care resource utilization including WPAI:SHP will be recorded.

Blood will be collected for central laboratory safety assessments, CRP and SAA, immunogenicity assessments, exploratory inflammatory biomarkers and IL-1Ra/anakinra serum concentration assessments.

Vital signs, physical examination and concomitant medication including rescue medication will be recorded. Adverse events will be recorded.

The compliance with the instructions for how to use the patient diary will be reviewed.

7.5.1.8 Day 28, Visit E

Visit E will only be performed at Day 28±2 days if no subsequent flare has occurred.

Adverse events and concomitant medication will be recorded. Blood will be collected for, immunogenicity assessments and IL-1Ra/anakinra serum concentration assessments.

7.5.1.9 Week 12, Visit 5

Visit 5 will only be performed at Week 12±5 days if no subsequent flare has occurred.

SAEs and outcomes of previously recorded AEs will be recorded and blood will be collected for CRP and SAA, immunogenicity assessments, exploratory inflammatory biomarkers and IL-1Ra/anakinra serum concentration assessments.

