The treatment period for each flare will consist of 4 to 6 visits to the study center. The visits are the screening/baseline visit (Visit 1/Day 1), the 72-hour visit (Visit 2/Day 4), the one-week visit (Visit 3/Day 8), the two-week visit (Visit 4/Day 15), the four-week visit (Visit E/Day 28) and the 3-month visit (Visit 5/Week 12). If a subsequent flare has been treated with IMP before Day 28 and/or Week 12 visit, the Day 28 and/or Week 12 visit will be cancelled.

A follow-up by phone will be performed at 24 and 48 hours post first IMP administration to remind the patients to complete the assessments and recordings in the eDiary. A follow-up by phone will also be performed every 12 weeks following Visit 5 of the latest flare.

The patient's participation in the study will be completed by an End-of-study follow-up by phone at the end of the extension period or at the Week 12 visit of the last flare treated with IMP in the study, whichever occurs latest.

All patients will be followed throughout the study, irrespective of treatment withdrawal or use of rescue medication.

At each baseline visit (first and subsequent flares), the joint that is most affected i.e., most painful will be defined as the index joint.

Rescue medication: Patients who have difficulty in tolerating their pain are allowed to take rescue medication after the 24-hour post-dose pain assessment but not within 6 hours before the 48- and 72-hour post-dose pain assessments. Permitted rescue medication includes topical ice/cold packs, paracetamol and/or codeine or short-acting tramadol.

Patients still having insufficient relief with the rescue medication listed above after the 72-hour post-dose pain assessment are allowed to take oral prednisone or prednisolone at a starting dose up to 0.5 mg/kg per day for a maximum of 5 days.

Number of patients planned:

A maximum of 169 patients can be randomized in this study. Initially 159 patients will be randomized, 53 to triamcinolone and 106 to anakinra (53 to 100 mg and 53 to 200 mg). For each randomized patient that have not contributed with any value for analysis of the primary endpoint (e.g. no value collected for patient-assessed pain intensity from baseline to 72 hours), one extra patient can be randomized in the study. A maximum of 10 extra patients can be randomized under this protocol.

Diagnosis and main criteria for inclusion:

Main inclusion criteria:

1. Signed informed consent to participate in this study.

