Visit 3 (Day 8): Blood sampling for central laboratory safety. Patient's assessment of pain intensity, patient's and physician's global assessment of response, physician's assessment of clinical signs, the patient's assessment of health related quality of life and health care resource utilization, assessments, immunogenicity assessments, inflammatory biomarkers and anakinra serum concentration assessments, vital signs, AEs and concomitant and rescue medication.

Visit 4 (Day 15): Patient's assessment of pain intensity, the patient's and physician's global assessment of response, the physician's assessment of clinical signs, the patient's assessment of health related quality of life and health care resource utilization.

Blood sampling for central laboratory safety assessments, immunogenicity assessments, inflammatory biomarkers and IL1ra/anakinra serum concentration assessments, physical examination and vital signs, AEs and concomitant and rescue medication.

Visit E (Day 28): Visit E will only be performed if no subsequent flare has occurred. Data will be collected on concomitant medication and adverse events. Blood will be collected for immunogenicity assessments and IL-1Ra/anakinra serum concentration assessments.

Visit 5 (Week 12): Visit 5 will only be performed if no subsequent flare has occurred. SAEs and outcomes of previously recorded AEs will be recorded and blood will be collected for immunogenicity assessments, inflammatory biomarkers and IL-1Ra/anakinra serum concentration assessments.

Follow up by telephone at every 12 weeks after Visit 5 of the latest flare (retention calls): A follow-up telephone call will be made to record outcomes of previously reported AEs and to encourage patient to remain in the study.

Subsequent flare(s):

Visits 1 to 5 (six visits; baseline, 72 hours, Day 8, Day 15, Day 28 and Week 12 after first IMP dose for subsequent flare): Assessments as described for Visits 1 to 5 above with the exception of informed consent, demographics (excluding weight) and randomization. Type of AEs to be collected will depend on time since last administration of IMP.

Follow-up by phone at 24 and 48 hours after first IMP dose for subsequent flare and at every 12 weeks after Visit 5 : Assessments as described for the first flare.

End of study:

End-of-study follow-up by phone will be performed either;

1. 52 weeks after randomization of the last patient in the study
or
2. 104 weeks after randomization of the individual patient

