7.1 Overall study design and plan

[figure not shown]
This is a randomized, double-blind, active-control, multicenter study to investigate the efficacy and safety of 2 doses of anakinra in the treatment of a gouty arthritis flare followed by an extension period to investigate the safety and efficacy of anakinra when treating subsequent flares.

The study consists of three periods: an optional pre-screening period, a double-blind treatment period and an extension period.

The treatment period of the first flare is double-blind, and the patients will be randomized to treatment with 100 mg anakinra, 200 mg anakinra or 40 mg triamcinolone in a 1:1:1 ratio. Anakinra will be administered as once daily s.c. injections for 5 days (Days 1 to 5) and triamcinolone as one i.m. injection (Day 1). The treatment period will be followed by an extension period. During this period the patients will receive the same treatment for subsequent flares occurring after Day 15 of the latest flare. The extension period will continue for all patients until 52 weeks after randomization of the last randomized patient in the study. However

the study treatment of an individual patient's flare will not start later than 2 years (104 weeks) after randomization of that patient. Thus the study will not exceed 104 + 12 weeks for any patient. Figure 1.

Figure 1 Study flow chart

When all patients have conducted the Day 15 visit of the first flare (Visit 4), the database will be locked and the primary analysis will be conducted. A second database lock will be conducted when all patients have completed the extension period.

The assessment period for each flare will consist of 4 to 6 visits to the study center. The visits are the screening/baseline visit (Visit 1/Day 1), the 72-hour visit (Visit 2/Day 4), the one-week visit (Visit 3/Day 8), the two-week visit (Visit 4/Day 15), the four week visit (Visit E/Day 28) and the 3-month visit (Visit 5/Week 12). If a subsequent flare has been treated before the Day 28 visit, the Day 28 and Week 12 visits will be cancelled. If a subsequent flare has been treated before the Week 12 visits that visit will be cancelled.

A follow-up by phone will be performed at 24 and 48 hours post first IMP administration to remind the patient to complete the assessments and recordings in the eDiary. A follow-up by phone will also be performed every 12 weeks following Visit 5 of the latest flare.

An end-of-study follow-up will be performed either;

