1. 52 weeks after randomization of the last patient in the study

or

2. 104 weeks after randomization of the individual patient

whichever occurs first.

If the IMP treatment started week 40 or later in case 1), or week 92 weeks in case 2), the Week 12 visit will replace the End-of-study follow-up by phone.

All patients will have their follow-up visits/phone calls, irrespective of treatment withdrawal or use of rescue medication.

Subsequent flares occurring before the Day 15 visit of the latest flare (Visit 4) will be treated with permitted rescue medication i.e., no IMP will be administered.

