7.5.3 Medical examination of current flare

Time of pain onset, the number and distribution of joints involved and index joint will be determined and recorded in the eCRF at Visit 1 of each flare.

The medical examination of subsequent flares will be recorded even if the patient is not eligible for IMP treatment of the current flare.

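### A new flare given no IMP stops the Day 28 and Week 12 visits and ADA samples under the visit sections, but not under the synopsis design text

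*Protocol*

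**What the plan says.** **Condition on occurrence.** Protocol 7.5.1.8 says "Visit E will only be performed at Day 28±2 days if no subsequent flare has occurred", and 7.5.1.9 says "Visit 5 will only be performed at Week 12±5 days if no subsequent flare has occurred". The synopsis visit list agrees: "Visit E will only be performed if no subsequent flare has occurred". The same condition is attached to the ADA and serum samples in the synopsis endpoint list, Protocol 6.2.1 (for serum, Week 12 only), 7.5.6.5 and 7.5.7.1, and SAP 3.3.3 and 3.3.4. Protocol 9.3.5.5 and SAP 17.5 limit the Week 12 exploratory biomarkers in the same way.

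**Condition on IMP treatment.** The synopsis design text cancels the visits on a different trigger: "If a subsequent flare has been treated with IMP before Day 28 and/or Week 12 visit".

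**Unclear condition.** Protocol 7.1 says "If a subsequent flare has been treated before the Day 28 visit, the Day 28 and Week 12 visits will be cancelled", and SAP 4.1 repeats this. Neither names IMP here. Protocol 7.1 also says "All patients will have their follow-up visits/phone calls, irrespective of treatment withdrawal or use of rescue medication".

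**Flares without IMP are foreseen.** Protocol 7.1 says "Subsequent flares occurring before the Day 15 visit of the latest flare (Visit 4) will be treated with permitted rescue medication", with no IMP given. Section 7.5.3 adds: "The medical examination of subsequent flares will be recorded even if the patient is not eligible for IMP treatment of the current flare".

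**The concern.** The two triggers give different instructions for a subsequent flare that gets no IMP. One cancels the last two visits of the current IMP course. The other keeps them.

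Section 7.2.1 gives safety and immunogenicity, rather than efficacy, as the main purpose of the extension. Section 5.3 warns that intermittent short courses may increase ADA formation, with possible allergic reactions or reduced efficacy. Day 28 and Week 12 are the late ADA samples after each course, and Day 28 is the last scheduled questioning about all adverse events.

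Under the occurrence wording these data would be missing selectively. The patients affected have flared again, and some may have been refused IMP because of infection or neutropenia (exclusion criteria 22 and 24).

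**Working it through.** The plan states no figure for this point, so there is none to reproduce. The check compares the rules and counts scheduled assessments.

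**1. Can *subsequent flare* mean only an IMP-treated flare?** No. Protocol 6.2 defines it as a flare occurring after the first one, within the study period. Sections 7.1 and 7.5.3 use the term for flares given no IMP. Two routes lead there:
- the flare comes before the Day 15 visit of the latest flare; or
- it fails a re-treatment criterion: inclusion 14–16 (3) or exclusion 21–29 (9), so 3 + 9 = 12 criteria.

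**2. What each text says for such a flare before Day 28**

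| Source | Trigger | Day 28 and Week 12 |
|---|---|---|
| 7.5.1.8, 7.5.1.9, synopsis visit list | flare occurred | visits not held |
| 7.5.6.5, 7.5.7.1, SAP 3.3.3–3.3.4 | flare occurred | samples not taken |
| Synopsis design text | flare treated with IMP | visits held |
| 7.1, SAP 4.1 | flare treated | held only if *treated* means with IMP |

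The synopsis therefore conflicts with itself as well as with the visit sections.

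**3. Is anything put in place of the lost visits?** Under the synopsis only a flare treated with IMP starts a new visit series. Under 7.5.6.1.2 only such a flare restarts adverse-event reporting. A flare without IMP brings no replacement ADA or serum samples.

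**4. Samples lost under the occurrence wording.** Post-dose ADA times (7.5.6.5) are Day 8, Day 15, Day 28 and Week 12, so 4. Post-dose serum times (7.5.7.1) are 72 hours and the same four, so 5.

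| New flare without IMP | ADA lost | Serum lost | Last ADA sample |
|---|---|---|---|
| Before Day 28 | 2 of 4 | 2 of 5 | Day 15: 2 weeks, not 12 |
| Between Day 28 and Week 12 | 1 of 4 | 1 of 5 | Day 28: 4 weeks, not 12 |

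The last column assumes that no later flare is treated with IMP.

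**5. Effect on ADA class (SAP 18.26), when sampling stops at Day 15**
- First positive at Day 28: the patient is counted as ADA negative.
- Treatment-induced positive at Days 8 and 15, negative at Week 12: the patient is classed as persistent instead of transient.
- First positive at Day 15: the patient is neither transient (last sample not negative) nor persistent (fewer than two sequential positives).

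SAP 16.6.2 tabulates adverse events by these classes.

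**6. Adverse-event questioning.** All adverse events are recorded to Day 28 (7.5.6.1.2), and the previous scheduled questioning is on Day 15. The most that can go unasked is 28 − 15 = 13 days (Days 16–28). Section 7.5.6.1.3 requires questioning at every clinic visit in the reporting period, so a site visit for the new flare after Day 15 shortens the gap. If that visit falls on Day 25, 28 − 25 = 3 days remain.

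**The case against.** The best reply is that the intended rule is evident and only the wording is loose. The synopsis design text is explicit. New visit series follow only IMP-treated flares. Follow-up continues despite rescue use. SAP 18.16 does not count a subsequent flare without treatment. The legible part of Appendix 2 footnote 2 speaks of a flare that occurred and was treated with IMP. This stands as evidence of intent, but sites work from the visit and sampling sections, and those say otherwise in several places. The footnote is incomplete in the text available, so it cannot settle the matter.

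A second reply is that ADA follow-up is cut short anyway whenever a new flare is treated with IMP. That is true, but such a flare brings its own sampling series. The flare without IMP does not.

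Third, harm needs a chain of events: a new flare within 12 weeks, no IMP for it, a site following the literal wording, and no later IMP-treated flare. This stands as a limit on how much can be claimed.

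Three stronger readings are tempting, and the documents do not support them:
- *That 7.1 plainly keeps the visits.* It says only *treated*, and it uses that word for rescue medication too. Its sentence on follow-up irrespective of rescue use favours keeping them but does not settle the question.
- *That a patient withdrawn from IMP for a related safety concern clearly loses the exit visit.* Section 7.3.3.1 bars further IMP for this patient, so 7.5.1.8 read alone would cancel Visit E after a new flare. But 7.3.3.2 encourages withdrawing patients to complete assessments up to Visit E of the last treated flare, and has safety withdrawals leave the study after Visit E. That points to holding the visit. The two sections conflict, and 7.5.1.8 does not clearly prevail.
- *That adverse-event information stops for 13 days.* Thirteen days is a maximum for scheduled questioning. SAE reporting to Week 12 and recording of spontaneous reports continue (7.5.6.1.2, 7.5.6.1.3), and related events are followed until resolved, chronic or stable (7.5.6.1.6).

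**Conclusion.** The inconsistency is real and worth correcting. For a subsequent flare given no IMP, a site following the occurrence wording loses up to 2 of 4 post-dose ADA samples and 2 of 5 post-dose serum samples, or 1 of 4 and 1 of 5 if the flare falls between Day 28 and Week 12. Nothing replaces those samples, and the patient's ADA class can change. The loss of adverse-event questioning is smaller and partly covered by other rules.

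These are losses per patient. They assume that the site applies the literal wording and, for the final ADA class, that no later IMP-treated flare adds samples. The documents give no rate of such flares, so no share of patients can be stated. The primary analysis does not use these visits and is unaffected.

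**What to change.** Replace the occurrence condition with *if no subsequent flare has been treated with IMP* in Protocol 7.5.1.8, 7.5.1.9, 6.2.1, 7.5.6.5 and 7.5.7.1, in the synopsis endpoint and visit lists, and in SAP 3.3.3 and 3.3.4. Align Protocol 9.3.5.5 and SAP 17.5, which describe summaries and do not instruct sites. In Protocol 7.1 and SAP 4.1, add *with IMP* after *treated* in the sentences that cancel visits. The rules on when IMP may be repeated stay as they are.

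Optionally, SAP 16.6.1 could report per flare how many patients have Day 28 and Week 12 ADA samples, and how many missed them after a flare given no IMP. The wording correction does not depend on this.

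The cost is one phrase in each named place. The visits retained are those the synopsis design text already plans.
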